## Revision history

Date of revision	Version	Summary of revisions made
February 28, 2019	1.0	Initial version
June 26, 2019	2.0	The subject population additionally includes the ICU patients.
August 1, 2019	3.0	Remove CRF from the attachments
August 2, 2019	3.1	Add ICU in the section 1.3

## Synopsis

**Title:** Evaluation of Capillary Refill Index

**Study type:** Single-center, cross-sectional study

**Subject population:** Adult emergency department (ED) and intensive care unit (ICU) patients (both males and females without regards to ethnic and racial backgrounds) who meet the following eligibility criteria will be recruited.

### Inclusion criteria

- Individuals 18 years of age or older
- Patients who present to the ED or who are admitted to the ICU of North Shore University Hospital (NSUH)

### Exclusion criteria

- Pregnant
- Prisoners
- Finger, hand or forearm anatomical anomaly or disease that may interfere with attaching a pulse oximeter sensor
- Patients' deemed clinically unstable by the clinical team

**Number of subjects:** Total number of subjects is up to 60.

**Study duration:**

- Expected duration of each subject participation is approximately 15 minutes.
- The duration of subject recruitment is anticipated for 6 months.
- The total duration of the study (including data collection and analysis) is approximately 1 year.

**Investigational device:** This study will use a non-significant risk combination of two components to measure Capillary Refill Index (CRI):

- Non-FDA-cleared pulse oximeter (OLV-4201A, Nihon Kohden Corporation, Tokyo, Japan): OLV-4201A pulse oximeter is intended for use in monitoring SpO2 and pulse rate (PR) using a finger sensor. It conforms to the safety standard of IEC 60601-1:2005+A1:2012, and the electromagnetic compatibility standard of IEC 60601-1-2:2007 and ISO 80601-2-61:2011 (clause202). The CRI measurement function is embedded in OLV-4201A.

- FDA-cleared SpO2 sensor probes (TL-271T3, Nihon Kohden Corporation, Tokyo, Japan): The sensors are disposable and intended for single patient use.

**Note:** the pulse oximeter is a class II device and is not used for life support or as a life sustaining device, thus the risk of this investigational use is considered extremely low. Furthermore, the device will not be used for any clinical diagnoses and any data obtained from the device will be blinded from the treating physicians and thus will not have any impact on the patient's clinical care. Therefore, the investigational device qualifies as a **non-significant risk (NSR) device** and **does not require an Investigational Device Exemption (IDE) approval** from the FDA.

**Objectives:****(1) Primary objective**

The primary objective is to evaluate the capability of Capillary Refill Index (CRI) measured by the investigational device to predict altered peripheral perfusion determined with visual Capillary Refill Time (CRT) test. Predictive capability of CRI needs to be assessed to achieve a goal to provide clinicians with an alternative method to the traditional CRT test.

**(2) Secondary objective(s)**

The secondary objective is to assess the correlation between CRI and CRT values. Although both CRI and CRT reflect time required for reperfusion of fingertip after the compression, measured absolute numerical values will be different since the mechanisms to assess peripheral perfusion are different between CRI and CRT.

**Endpoint(s):****(1) Primary endpoint**

The primary endpoint is the area under the curve (AUC) of the receiver operator characteristic (ROC) curve analysis on CRI values to predict the altered peripheral perfusion determined with the CRT test. A specific cutoff value for CRI has not yet been determined, then the AUC value will be used to summarize comprehensive capability of CRI to detect the altered peripheral perfusion.

**(2) Secondary endpoint(s)**

The secondary endpoints include the followings:

- Sensitivity and specificity of CRI in differentiating altered peripheral perfusion determined with the CRT test. An optimal cutoff value for CRI will be

determined with the ROC analysis for the primary endpoint.

- Pearson's or Spearman's correlation coefficient to assess the correlation between CRI and CRT values.

## List of Abbreviations

CRI	Capillary Refill Index
CRT	Capillary Refill Time
CIP	Clinical investigation plan
PI	Principal investigator
FDA	Food and Drug Administration
IDE	Investigational Device Exemption
NSR	Non-significant risk
°C	Degrees Celsius
°F	Degrees Fahrenheit
SpO 2	Peripheral capillary oxygen saturation
PR	Pulse rate
NKC	Nihon Kohden Corporation
FIMR	Feinstein Institute for Medical Research
NSUH	North Shore University Hospital
IRB	Institutional Review Board
ED	Emergency department
ICU	Intensive care unit
AE	Adverse event
PHI	Personal Health Information
CRF	Case Report Form

## 1 General

### 1.1 Introduction

Capillary refill time (CRT) test is a simple and noninvasive method typically used to assess peripheral blood perfusion at the bedside. CRT is defined as the time required for a distal capillary bed (e.g., fingertip) to regain its color after having received enough compression to cause blanching [1]. A prolonged CRT (e.g. over 2 seconds) suggests a decrease in peripheral perfusion and is used to identify hemodynamically compromised patients in the critical care setting. Several observational studies have reported the clinical usefulness of CRT and the relevance between prolonged CRT and critical conditions. In intensive care patients, prolonged CRT was associated with diminished tissue perfusion as well as an increase in organ dysfunction with high blood lactate levels [2]. Prolonged CRT was also associated with the development of severe complications in patients following abdominal surgery [3]. However, the conventional CRT test has limitations in objectivity given that the measurement depends on clinicians' subjective visual assessment. Since the repeatability and inter-rater agreement of the CRT test has been questioned over the last few decades [4, 5], there is great demand for the creation of objective methods to assess peripheral blood perfusion [5, 6].

We developed a new analytic method to assess peripheral blood perfusion quantitatively using pulse oximetry waveforms to provide clinicians with an alternative method to the traditional CRT test. The method calculates the time it takes for blood to return to the fingertip after release from compression by algorithmically analyzing the light intensity waveform of a normal pulse oximeter sensor attached to a patient's fingertip [7,8]. Since the mechanisms to assess peripheral blood perfusion are different from the traditional CRT tests, we differentiate the calculated number by our method from CRT and named it Capillary Refill Index (CRI). The CRI measurement function is embedded in our investigational device OLV-4201A pulse oximeter.

## 2 Investigational device

### 2.1 Summary description of the investigational device and its intended purpose

This study will use a **non-significant risk** combination of two components:

- Non-FDA-cleared pulse oximeter (OLV-4201A, Nihon Kohden Corporation, Tokyo, Japan): See *Attachment 1 Operator's Manual of OLV-4201*. OLV-4201A pulse oximeter is intended for use in monitoring SpO2 and pulse rate (PR) using a finger sensor. It conforms to the safety standard of IEC60601-1:2005+A1:2012, and the electromagnetic compatibility standard of IEC 60601-1-2:2007 and ISO 80601-2-61:2011 (clause202). See *Attachment 2 and 3 Certificate of Safety/EMC Test*.
- FDA-cleared SpO2 sensor probe (TL-271T3, Nihon Kohden Corporation, Tokyo, Japan; K151080, K120888, K080342, K001693, K946175, K945578, K043517, K082785): See *Attachment 4 Operator's Manual of SpO2 sensor probe*. The sensor is disposable and intended for single patient use.

The investigational device passes light of two wavelengths (red: 660 nm, infrared: 940 nm) through the fingertip and measures the light intensity at each wavelength, allowing it to determine the different concentrations of two types of hemoglobin (oxy-hemoglobin and deoxy-hemoglobin). The CRI measurement uses a wavelength of infrared (940 nm) to trace change of blood volume in the fingertip. To measure CRI, a patient's fingertip with a pulse oximeter sensor probe attached is briefly compressed by an operator. The light intensity transmitted through the fingertip increases during compression as blood, which is the major absorber of the light, is squeezed out of the fingertip. The compression phase is followed by the release phase during which the light intensity decreases with return of blood to the fingertip. The curve describing the recovery phase of the intensity waveform is modeled as an exponential decay using the least squares method. The time for returning to a predetermined level of the intensity is calculated as CRI (Figure 1). The detailed operation of the CRI function of OLV-4201A is described in *Attachment 5 Operator's Manual of the CRI function*.

**Figure 1:** Calculation of CRI using a pulse oximeter waveform

**Note:** the pulse oximeter is a class II device and is not used for life support or as a life sustaining device, thus the risk of this investigational use is considered extremely low. Furthermore, the device will not be used for any clinical diagnoses and any data obtained from the device will be blinded from the treating physician and thus will not have any impact on the patient's clinical care. Therefore, the investigational device qualifies as a **non-significant risk (NSR) device** and **does not require an Investigational Device Exemption (IDE) approval** from the FDA.

## 2.3 Name or number of the model/type including software version and accessories

- (1) Model number: OLV-4201A
- (2) Name: Pulse Oximeter
- (3) Software version: 01-06
- (4) Composition

No.	Name	Model number
1	Pulse Oximeter	OLV-4201A

- (5) Accessories and disposables

No.	Name	Model number
1	Power cord	
2	SpO 2 connection cord	JL-400T
3	Disposable SpO 2 sensor probe	TL-271T3

## 2.4 Traceability

- OLV-4201A Pulse Oximeter: identify with assigned serial numbers
- TL-271T3 SpO2 sensor probe: identify with assigned lot numbers

## 2.5 Intended purpose of the investigational device in this clinical investigation

- Measurement of CRI

## 2.6 Populations and indications for which the investigational device is intended

- Adult ED and ICU patients both males and females aged 18 years or older

## 2.7 Materials of the investigational device contacting with tissues or body fluids

Material of the investigational device that will be in contact with tissues is as follows:

TL-271T3 SpO2 sensor probe

Name of parts	Material
Sensor portion	Polyester

There is no material that will be in contact with body fluids.

## 2.8 Necessary training and experience needed to use the investigational device

Investigators will be trained by sponsor representatives about operations and cleaning of the investigational device following the operator's manual of the investigational device.

## 2.9 Specific medical or surgical procedures involved in the use of the investigational device

There is no medical nor surgical procedure involved in the use of the investigational device.

## 3 Justification for the design of the clinical investigation

### 3.1 Evaluation of the results of the relevant pre-clinical testing/assessment carried out to justify the use of the investigational device in human subjects

OLV-4201A Pulse Oximeter conforms to the safety standard of IEC60601-1:2005+A1:2012, and the electromagnetic compatibility standard of IEC 60601-1-2:2007 and ISO 80601-2-61:2011(clause202). See *Attachment 2 and 3 Certificate of Safety/EMC Test*. The part of the investigational device that will be in contact with the human subjects is the FDA-cleared TL-271T3 SpO2 probe. There has been no issue regarding biocompatibility of the material of the SpO2 probe described in the section 2.7. Therefore, the use of the investigational device in human subjects in this clinical investigation is considered to be justified.

### 3.2 Evaluation of clinical data relevant to this clinical investigation

*Attachment 6* is a report of a previous clinical study conducted at the ED of NSUH. In this preliminary clinical study, the term "Blood Refill Time (BRT)" was used, which is the same as CRI, and a prototype device was used to measure BRT. The prototype device is a non-FDA-cleared pulse oximeter (OLV-3100, Nihon Kohden Corporation, Tokyo, Japan) which is a previous model of OLV-4201A. OLV-3100 was used to record the pulse oximetry waveforms, and the recorded waveforms were analyzed thereafter. The calculation of CRI used in the analysis is the same as the CRI function embedded in the investigational device. A convenience sample of thirty adult ED patients were enrolled as subjects. Visual CRT values were measured by an ED physician using a stopwatch. Area under the receiver operator characteristic curve of BRT to predict whether the visual CRT was greater than 2.0 seconds was 0.84 (95% CI 0.70-0.98). There was a strong correlation between BRT and CRT ( $r=0.723$ ,  $p<0.001$ ). The results suggest that BRT measurements with the prototype device successfully identified subjects with altered peripheral perfusion determined by the conventional visual assessment of CRT.

## 4 Risks and benefits of the investigational device and the clinical investigation

### 4.1 Anticipated clinical benefits

This study is not expected to directly benefit the subjects, but it will provide information that may assist in improving the method to assess peripheral blood perfusion quantitatively.

### 4.2 Anticipated adverse device effects

There is no particular anticipated adverse device effect since the applied part of the investigational device (TL-271T3 SpO2 sensor probe) is equivalent to standard pulse oximeter sensors and has a FDA approval. A well-known potential adverse effect of pulse oximeters is thermal injuries due to temperature rise at the applied part of the sensor.

### 4.3 Residual risks associated with the investigational device identified in the risk analysis

There is no residual risk associated with the investigational device which is judged unacceptable.

### 4.4 Risk associated with participation in the clinical investigation

There is a potential risk of breach of confidentiality, which will be minimized by following the procedures set forth in the section 8 "Data management" of this CIP.

The study procedures are no greater than minimal risk. The pulse oximeter is a class II device and is not used for life support or as a life sustaining device, thus the risk of this investigational use is considered extremely low. Furthermore, the device will not be used for any clinical diagnoses and any data obtained from the device will be blinded from treating physicians and thus will not have any impact on the subject's clinical care. The application of the sensor probe on the subject's finger is not expected to cause pain. If the study procedure becomes too uncomfortable, the procedure will be stopped immediately. The investigator (qualified ED physician) will assess the clinical status of the subject prior to enrollment to determine eligibility when the subject is recruited.

### 4.5 Possible interactions with concomitant medical treatments

There is no possible interaction with concomitant medical treatments.

### 4.6 Steps that will be taken to control or mitigate the risks

All data and records generated during this study will be kept confidentially in accordance with policies of the study site(s) and HIPAA on subject privacy, and the investigator and other site personnel will not use such data and records for any purpose other than conducting the study. All subjects will be given a unique study number. The PI will be responsible for ensuring the safety of the subjects participating in this study. The study team will report to the PI any time that the sensor has to be removed prematurely, and the PI will track this information. Thermal injuries which are the potential adverse effect of the pulse oximeter will be assessed after the measurements with the investigational device.

#### 4.7 Risk-to-benefit rational

Based on the discussions above and the minimal risk involved with the study, the scientific benefits of this study outweigh the risks, even though no benefit for each individual study participant is expected.

### 5 Objectives and hypotheses of the clinical investigation

#### 5.1 Primary and secondary objectives

##### 5.1.1 Primary objective

The primary objective is to evaluate the capability of CRI to predict altered peripheral perfusion determined with the CRT test. Predictive capability of CRI needs to be assessed to achieve a goal to provide clinicians with an alternative method to the traditional CRT test. Receiver operator characteristic (ROC) curve analysis will be performed and area under the curve (AUC) will be calculated for this objective. An optimal cutoff value for CRI will be determined with the ROC analysis and the sensitivity and the specificity in differentiating altered peripheral perfusion will also be calculated.

##### 5.1.2 Secondary objective(s)

The secondary objective is to assess the correlation between CRI and CRT values. Although both CRI and CRT reflect time required for reperfusion of fingertip after the compression, measured absolute numerical values will be different since the mechanisms to assess peripheral perfusion are different between CRI and CRT. Pearson's correlation coefficient will be calculated to assess the correlation between CRI and CRT values. If the values are not normally distributed, Spearman's correlation coefficient will be used instead.

#### 5.2 Hypotheses to be tested by statistical data from the clinical investigations

CRI is capable to detect subjects with altered peripheral perfusion determined with the CRT test.

#### 5.3 Claims and intended performance of the investigational device that are to be verified

##### (1) Capillary Refill Index (CRI)

- Display range: 0.1 ~ 99.9 seconds

\*CRI will not be claimed as an intended for use in a regulatory application for FDA clearance of OLV-4201A Pulse Oximeter. CRI will be included in the regulatory application as an index intended for clinical research only, not for diagnosis.

#### 5.4 Risks and anticipated adverse device effects to be assessed

##### (1) Thermal injuries due to temperature rise at the applied part of the sensor probe

## 6 Design of the clinical investigation

### 6.1 General

#### 6.1.1 Type of the clinical investigation

Single-center, cross-sectional study:

In this clinical investigation, CRI and CRT measured at a same time point for each will be compared.

#### 6.1.2 Measures to be taken to minimize or avoid bias, including randomization and blinding/masking

- The investigator who will measure the visual CRT will be blinded from the CRI values measured with the investigational device.
- CRI and CRT measurements will be alternately repeated for 3 times each per a subject, and each averaged value will be used as measured CRI and CRT values for each subject.

#### 6.1.3 Primary and secondary endpoints

##### (1) Primary endpoint

The primary endpoint is the area under the curve (AUC) of the receiver operator characteristic (ROC) curve analysis on CRI values to predict the altered peripheral perfusion determined with the CRT test. A specific cutoff value for CRI has not yet been determined, then the AUC value will be used to summarize comprehensive capability of CRI to detect the altered peripheral perfusion. Procedures of the measurement of CRI and CRT, and statistical methods are described in the section 6.4 "Procedures" and the section 7 "Statistical considerations", respectively.

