#### **Visual CRT measurement using a stopwatch**

An investigator (an ED physician) will compress the fingertip of the subject's index or middle finger for five seconds, signaled by "start compression" and "release compression" beep sounds. When the fingertip is released from the compression, the investigator will begin the visual CRT measurement. The investigator will hold a stopwatch in the hand that does not perform the compression and use this stopwatch to measure CRT.

[figure not shown]

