## 7 Statistical considerations

### 7.1 Statistical design, method and analytical procedures

In order to assess the study aims and hypotheses, we will describe the study sample using descriptive statistics such as frequencies, proportions, means, standard deviations, 95% confidence intervals, medians, and interquartile ranges. The mean of the three repeated CRI and CRT measurements will be considered as the values for each subject.

The primary and secondary endpoints are described in the section 6.1.3. Receiver operator characteristic (ROC) curve analysis will be performed and area under the curve (AUC) will be calculated to demonstrate capability of CRI to predict altered peripheral perfusion determined with the CRT test. An optimal cutoff value for CRI will be determined with the ROC analysis and the sensitivity and the specificity in differentiating altered peripheral perfusion will be calculated. Pearson's, or Spearman's correlation coefficient will be calculated to assess the correlation between CRI and CRT values.

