## 7.2 Sample size

The primary endpoint of this study is an AUC of the ROC curve analysis on CRI values to predict altered peripheral perfusion determined with the CRT test. Sample size for subjects with altered peripheral perfusion required to obtain desired AUC is calculated with the following equation [9]:

$$n = \frac{Z_{\alpha/2}^2 \times V(AUC)}{d^2}$$

where,  $Z$  is the standard normal deviate determined with probability of type I error:  $\alpha$ ,  $d$  is the desired width of one-half of the confidence interval (CI), and  $V(AUC)$  is variance of AUC which is derived from the following equation [10]:

$$V(AUC) = (0.0099 \times e^{-a^2/2}) \times \{(5a^2 + 8) + (a^2 + 8)/\kappa\}$$

where,  $a = \varphi^{-1}(AUC) \times 1.414$ ;  $\varphi^{-1}$  is inverse of standard cumulative normal distribution; and  $\kappa$  is the ratio of the number of subjects without the altered peripheral perfusion to the number of subjects with the altered peripheral perfusion. Based upon our preliminary data:

- The prevalence of the subjects with altered peripheral perfusion is expected to be 30%, and then  $\kappa$  is 2.33.
- We hypothesize that the AUC will be 0.84, and then  $a = \varphi^{-1}(0.84) \times 1.414 = 1.406$ .

Therefore,  $V(AUC)$  can be calculated as follow:

$$V(AUC) = (0.0099 \times e^{-1.406^2/2}) \times \{(5 \times 1.406^2 + 8) + (1.406^2 + 8)/2.33\} = 0.0816$$

To achieve an AUC of at least 0.70 which is considered as fair [11], one-half of the CI:  $d$  should be 0.14 with the hypothesized AUC of 0.84. At the significance level of 5% (probability of type I error:  $\alpha = 0.05$ ), the number of subjects with altered peripheral perfusion is derived as:

$$n = \frac{Z_{\alpha/2}^2 \times V(AUC)}{d^2} = \frac{1.96^2 \times 0.0816}{0.14^2} = 15.99 \approx 16$$

The total number of required sample size given by  $n(1 + \kappa)$  is 54. Considering possible early withdrawals of subjects, we plan to recruit up to 60 subjects to achieve 54 evaluable subjects (10% of drop-out rate).

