#### 7.5 Pass/fail criteria to be applied to the results of the clinical investigation

The hypothesis to be tested in this study is that CRI is capable to detect subjects with altered peripheral perfusion determined with the CRT test, as described in the section 5.2. A criterion to accept the hypothesis is that the AUC value described in the section 6.1.3 (1) "Primary endpoint" is at least 0.70 which is considered as fair [11].

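### Does the lack of a stated CRT cutoff in Sections 6.1.3, 7.1 and 7.5 leave the primary AUC undefined?

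*Combined protocol and SAP*

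**What the plan says.** Section 6.1.3 (1) makes the primary endpoint an AUC on "CRI values to predict the altered peripheral perfusion determined with the CRT test". For detail it sends the reader onward: "Procedures of the measurement of CRI and CRT, and statistical methods are described in the section 6.4" and Section 7. Section 7.1 sends the reader back: "The primary and secondary endpoints are described in the section 6.1.3". Section 7.5 accepts the hypothesis if the AUC described in 6.1.3 (1) is at least 0.70.

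Section 6.4.1 covers the timing of CRT ("When the fingertip is released from the compression, the investigator will begin the visual CRT measurement") and gives no value that counts as abnormal. Sections 6.1.2 and 7.1 make the mean of three readings each subject's value. The remark in 6.1.3 that a cutoff is still undetermined concerns CRI, the index test, and not CRT.

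A CRT value in seconds appears in two places. Section 1.1 says: "A prolonged CRT (e.g. over 2 seconds) suggests a decrease in peripheral perfusion". Section 3.2 reports the pilot AUC "to predict whether the visual CRT was greater than 2.0 seconds" as 0.84 (95% CI 0.70-0.98), and goes on to describe this as identifying subjects with altered peripheral perfusion. Section 7.2 takes an AUC of 0.84 and a prevalence of 30%, and attributes both to preliminary data.

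**The concern.** An ROC curve cannot be drawn until every subject is classed as positive or negative on the reference test. Here that means putting a number of seconds on CRT. A reader who follows the cross-references from 6.1.3 to 6.4 and 7, and from 7.1 and 7.5 back to 6.1.3, finds no such number.

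The primary AUC, its 0.70 criterion, the sensitivity and the specificity all depend on this classification. So do the inputs to the sample size. Section 16.2 limits blinding to the bedside measurements, and Sections 6.5 and 8.1 (4) have the principal investigator reviewing aggregate data throughout. If the cutoff were really open, it could be settled with CRI and CRT both in view, and the reader of the report could not tell from the endpoint section that it had been fixed beforehand.

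**Working it through.** **1. Which cutoffs does the document offer?** Setting the sections side by side:

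- 6.1.3, 6.4.1, 7.1, 7.2, 7.5: no CRT value.
- 1.1: over 2 seconds, as an example.
- 3.2: greater than 2.0 seconds, as the pilot's definition.

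There is one candidate, given as a strict inequality both times and contradicted nowhere. Section 3.2 joins it to the same term that the endpoint uses, and its 0.84 is the AUC in 7.2. That the 30% rests on the same cutoff is a reasonable inference: 3.2 does not report a prevalence, and the pilot report is an attachment that was not available for this review.

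**2. Does 7.2 reproduce?** Inputs from 7.2: AUC 0.84, κ = 2.33, d = 0.14, Z = 1.96.

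- a = 1.414 × z(0.84) = 1.406
- V = 0.0099 × exp(−a²/2) × {(5a² + 8) + (a² + 8)/κ} = 0.08166 (plan: 0.0816)
- n = 1.96² × V/0.14² = 16.005 (plan: 15.99, taken as 16)
- total = 16 × 3.33 = 53.3, rounded up to 54; 54/0.9 = 60

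The plan's figures hold up to rounding. Confirming 2.0 s with 30% prevalence would leave 16, 54 and 60 as they are.

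**3. What if another cutoff changed the prevalence?** Let p be the share classed as altered, so κ = (1 − p)/p. With 54 subjects and AUC held at 0.84, half-width = 1.96 × √(V/(54p)), and the total needed for 0.14 is n(1 + κ). The documents do not give the CRT distribution, so p is an assumed range.

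| p | κ | V | Positives of 54 | Half-width | Total for 0.14 |
|---|---|---|---|---|---|
| 20% | 4.00 | 0.0751 | 10.8 | 0.163 | 73.6 |
| 30% | 2.33 | 0.0816 | 16.2 | 0.139 | 53.3 |
| 50% | 1.00 | 0.1026 | 27.0 | 0.121 | 40.2 |

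These figures describe precision. Section 7.5 asks for an AUC of at least 0.70 and mentions no confidence limit, so the half-width does not enter the decision.

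**4. Would the AUC itself move?** Assume that CRI and CRT are bivariate normal with the pilot correlation of 0.723 (400,000 simulated subjects). The AUC is then 0.883, 0.860, 0.848, 0.843 and 0.842 when 10%, 20%, 30%, 40% and 50% are classed as altered. In this model no cutoff in that range brings the expected AUC near 0.70.

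**The case for a change.** The strongest case for a change is that an inferable value is not a prespecified one. Section 1.1 offers 2 s only as an example, and Section 3.2 says what an earlier study of thirty patients did with a prototype. Neither says that this study will do the same. Sections 7.8, 9 and 10.2 require modifications and deviations to be documented, approved or discussed, but they work less well on a value never formally set. One sentence would remove the doubt.

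The possible harm can be illustrated by simulating a deliberate search. Assume log-normal CRT with 30% above 2.0 s, 54 subjects, and the best AUC taken from cutoffs of 1.5, 2.0, 2.5 and 3.0 s. Compared with 2.0 s fixed, the chance of reaching 0.70 rises from about 1% to 6% with no association, and from about 25% to 51% at a mean AUC of 0.64. At the pilot correlation it is 99% or more either way, while the mean reported AUC rises from 0.85 to 0.90.

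Of this, the drafting point stands: naming the cutoff in the endpoint section is better practice. The simulated harm carries little weight. Nothing in the documents suggests such a search, and the CRT distribution is invented. Part of the rise from 25% to 51% is not selection, because the true AUC in that model is higher at higher cutoffs: 2.5 s fixed in advance already gives about 31-39%. At the planned effect the decision barely moves.

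**Conclusion.** No change follows. The cutoff is missing from the sections where a reader looks first, but the document supplies a single value, links it to the endpoint's own term, and plans the study on the AUC obtained with it. An analyst would class a subject as altered when the mean CRT exceeds 2.0 s, and use of the mean is already specified. Writing the value into 6.1.3 would repeat it without altering the procedures, the sample size or the expected result.

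The conclusion rests on two readings: that the pilot definition carries over to this study, which nothing contradicts, and that the 30% belongs to the same cutoff, which is inferred. If the second were wrong, the half-width at 54 subjects would shift by about 0.02 either way across prevalences of 20% to 50%, and the 7.5 criterion would read the same. The documents do not show that following the plan would give a wrong answer.
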